## **8.3 Statistical analysis plan**

A detailed statistical analysis plan shall be written and finalized prior to the lock of the study database.

All statistical analyses, that were not pre-specified in the protocol or the statistical analysis plan and were conducted after database lock, will be considered as additional/exploratory analyses.

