## Synopsis

Title	Phase-I/II trial for relapsed or refractory AML patients combining cytarabine and mitoxantrone with venetoclax (RELAX)
Short Title	RELAX
Target population	Patients with acute myeloid leukemia (AML) at first or second relapse after intensive chemotherapy including allogeneic stem cell transplantation or primary refractory to standard induction chemotherapy who are eligible for intensive salvage treatment
Study design	Open-label, multi-center, single-arm, phase I/II study
Sponsor	Technische Universität Dresden, [name]
Coordinating Investigator	[name]. med. [name] Medizinische Klinik und Poliklinik I, Universitätsklinikum TU Dresden [name] [contact] [contact]
Protocol Committee	[name] [contact] [name]. med. [name] [name] Medizinische Klinik und Poliklinik I, Universitätsklinikum TU Dresden [name]
Objectives of the Trial	To determine safety, tolerability, maximum tolerated dose, and recommended phase II dose of venetoclax in combination with increasing cytarabine doses plus fixed dose mitoxantrone in subjects with a relapsed or refractory AML considered fit for intensive salvage therapy.  To assess the preliminary efficacy of venetoclax in combination with increasing cytarabine doses plus fixed dose mitoxantrone in subjects with a relapsed or refractory AML considered fit for intensive salvage therapy.

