#### 8.1.4 Statistical methods

The analysis of the phase I trial part will be of descriptive nature. It will be based on the first treatment cycle. Further treatment cycles will not be considered for determination of MTD. Changes to the analyses, specified in this protocol, will be described in a detailed statistical analysis plan.

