## **8.2 Phase II – Expansion part**

### **8.2.1 Sample size**

In combination with low-dose cytarabine, the bcl2 inhibitor venetoclax has shown promising clinical activity with a CR+CRi rate of 54% in a frail elderly patient population receiving initial treatment for newly diagnosed AML(Wei et al., J Clin Oncol 2019). In addition, cytarabine may synergize with venetoclax by down-regulating Mcl-1. In a paper from 2011, Touzeau et al. showed synergy between ABT-737 and Ara-C in mantle cell lymphoma cell lines (Touzeau et al., Clin Cancer Res 2011).

We hypothesize that the combination of intermediate-dose cytarabine salvage plus venetoclax will have an increased antileukemic efficacy compared to standard salvage alone and that efficacy signals can already be shown in a small patient number in a phase-I/II expansion cohort. Historical data show: While only around 20% of frail patients who have been treated with low –dose cytarabine alone reach CRs, the combination with venetoclax results in an increase by 30% (Burnett 2007). Standard intensive relapse treatments produce CR rates of around 40-55% (Steinmetz et al., Ann Hematol 1999; Karanes et al., Leuk Res 1999; Pastore et al., Ann Hematol 2003; Larsson et al., Leukemia & Lymphoma 2012; Fiegl et al., Leukemia 2014; Ahmed et al., Leuk Res 2015; Thiel et al., Ann Oncol 2015; Bergua et al., Br J Haematol 2016). Assuming a similar beneficial effect of venetoclax in this setting, we assume a CR rate of 65% for the combination treatment of intermediate-dose cytarabine, mitoxantrone and venetoclax.

The phase II part will be performed as single stage study according to A'Hern (A'Hern Stat Med 2001). It will test the null hypothesis that the CR/CRi rate is  $\leq 45\%$ . This benchmark for the CR/CRi rate was selected based on literature review of trials for this patient population. We expect a CR/CRi rate of 65% with the combination treatment as the minimum required level of efficacy. This expectation is based on CR/CRi rates reported for the combination of venetoclax and demethylating agents in patients with de novo AML being around 70% (DiNardo ASH 2015, Pollyea ASCO 2016). To be able to reject the null hypothesis ( $H_0: p \leq 0.45$ ) in favor of the alternative hypothesis ( $H_1: p \geq 0.65$ ) at a one-sided significance level of 5% with 80% power 42 patients must be enrolled.

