### **9.3 Data processing**

Data management is performed by the Data Center of the SAL Studienzentrale and the KKS Dresden by means current version of study software MACRO. Data quality will be checked by programmed range checks, validity checks, and consistency checks. In addition, a manual/visual data check for medicinal plausibility is done according to GCP guidelines. There might be discrepancies, which are to be clarified by authorized persons by means of the study software.

After the study is finished and before data are analyzed, a meeting will be held between the sponsor and statistician. When the database has been declared to be complete and accurate, it will be locked. This procedure has to be documented.

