## 12 Amendments

Any change or addition to this protocol requires a written protocol amendment which must be approved and signed by the sponsor and the investigator before implementation. Amendments significantly affecting the safety of patients, the scope of the investigation, or the scientific quality of the study require additional approval by the IEC, and by the federal regulatory authority (BfArM). A copy of the written approval of the IEC and CA must be given to the monitor. Examples of amendments requiring such approval are:

1. An increase in drug dosage or duration of exposure of patients,
2. A significant change in the study design (e.g., addition or deletion of a control group, inclusion/exclusion criteria),
3. An increase in the number of invasive procedures to which patients are exposed,
4. Addition or deletion of a test procedure for safety monitoring.

These requirements for approval should in no way prevent any immediate action from being taken by the investigator or by the sponsor in the interests of preserving the safety of all patients included in the trial. If an immediate change to the protocol is felt to be necessary by the investigator and is implemented by him/her for safety reasons, the sponsor should be notified and the IEC at the center should be informed within 10 working days. Actions against immediate danger needs to be reported **immediately** to the CA, local authority, and EC (GCP-V §13 (5)).

Amendments affecting only administrative aspects of the study do not require formal protocol amendments or IEC approval, but the IEC must be kept informed of such administrative changes. Examples of administrative changes not requiring formal protocol amendments and IEC approval include:

1. Changes in the staff used to monitor trials (e.g., Sponsor staff versus a CRO),
2. Minor changes in the packaging or labeling of study drug.

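### The phase II analysis-set denominator is left open, and the SAP may settle it up to database lock, long after the open-label responses are known

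*Protocol*

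**What the plan says.** The Synopsis describes the design as "Open-label, multi-center, single-arm, phase I/II study". Section 6.4 bases response on local results and uses central review for quality control only.

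On the SAP, section 8.3 states: "A detailed statistical analysis plan shall be written and finalized prior to the lock of the study database". Its next sentence classes as additional or exploratory those analyses that "were not pre-specified in the protocol or the statistical analysis plan and were conducted after database lock". Section 9.3 adds: "After the study is finished and before data are analyzed, a meeting will be held between the sponsor and statistician"; it then describes the lock.

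On changes, section 8.1.4 (phase I methods) reads: "Changes to the analyses, specified in this protocol, will be described in a detailed statistical analysis plan". Section 12 reads: "Any change or addition to this protocol requires a written protocol amendment". Section 8.2 has no counterpart to the sentence in 8.1.4.

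On the phase II primary analysis, the protocol fixes the endpoint (8.2.3.1), the null rate of 45% with a one-sided 5% exact binomial test (8.2.1, 8.2.5.1), missing outcome as failure (8.2.4.2), the full analysis set (FAS) as primary with the per-protocol set as sensitivity (8.2.5), no centre adjustment in the primary analysis (8.2.4.3) and a single analysis (8.2.4.4).

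On who is in the FAS, three places differ:
- Section 4.4.1 defines a dropout as a patient who stops treatment after at least one dose of study drug, places dropouts in the FAS and refers to 8.2.2.1.
- Section 8.2.2.1 requires exposure to both venetoclax and cytarabine at the MTD, and includes phase I patients treated at the MTD.
- The Synopsis takes the phase II FAS as denominator but states the rejection rule as 25 responders among 42 patients. Section 3.3 describes those 42 as additional to phase I.

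**The concern.** Finalising a SAP before lock protects a trial in which outcomes or allocation stay hidden until then. Here the sites know each response when it is read, and nothing is randomised or masked. Any detail of the primary analysis left to the SAP can therefore be decided with the result in view.

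The detail left open is the denominator of the one confirmatory test. Venetoclax, which section 5.1.1 calls the study drug, starts on day 1; cytarabine starts on day 4 (section 5.4.1). A patient who stops on days 1 to 3 is in the FAS under 4.4.1 and outside it under 8.2.2.1. If such a patient has no remission, the choice removes or keeps a failure. Phase II patients are not replaced (4.4.2), so the denominator really does shrink. Whether phase I patients at the MTD count, and against which cut-off, is a second open choice. With about 42 patients, one or two can decide the result.

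Two wording problems add to this. Read literally, the last sentence of 8.3 labels an unplanned analysis only if it was run after lock, so one run earlier carries no label. And 8.1.4 sends changes to protocol analyses to the SAP, while section 12 asks for an amendment.

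**Working it through.** **Inputs.** Null rate p0 = 0.45, alternative p1 = 0.65, one-sided 5%, 80% power, N = 42 (section 8.2.1); rejection at 25 responders (Synopsis). All tail probabilities are exact binomial: P(X ≥ r | n, p) = Σ C(n,x) p^x (1−p)^(n−x), summed over x = r to n.

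**1. The plan's own figure.** P(X ≥ 25 | 42, 0.45) = 0.0415 and P(X ≥ 25 | 42, 0.65) = 0.818. The design reproduces, and 42 is the smallest n whose exact 5% test reaches 80% power.

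**2. Timing.** Recruitment lasts 24 months and first patient in to last patient out is 48 months (Synopsis). Remission is assessed by day 45 at the latest (6.4.2.2), about 1.5 months. The last primary outcome is known near month 24 + 1.5 = 25.5. If lock follows last patient out, the gap is 48 − 25.5 = 22.5 months. The protocol does not date the lock, so this is an assumption.

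**3. Early-stopping failures counted in or out.** With 24 responders at p0:
- 24/42: P(X ≥ 24 | 42) = 0.0772, not significant.
- 24/41: P(X ≥ 24 | 41) = 0.0568, not significant; one exclusion is not enough.
- 24/40: P(X ≥ 24 | 40) = 0.0405, significant.

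If two failures who stopped on days 1 to 3 could be counted either way once the result is known, 24 responders suffice. The one-sided error then rises from 0.0415 to at most P(X ≥ 24 | 42, 0.45) = 0.0772. If instead exactly two of the 42 are certain failures and the overall rate stays at 45%, the other 40 respond at 0.45 × 42/40 = 0.4725, and P(X ≥ 24 | 40, 0.4725) = 0.0726.

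**4. Phase I patients at the MTD counted in or out.** Assume m = 3 or 6 such patients, the cohort sizes of the 3+3 scheme. The exact 5% critical values are 27/45 (error 0.0308) and 28/48 (error 0.0438). With X from the 42 and Y from the m added patients, taking whichever set rejects has error P(X ≥ 25 or X + Y ≥ r), where r = 27 or 28:
- m = 3: 0.0448
- m = 6: 0.0551

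**5. The cut-off of 25 carried over to the larger set.**
- P(X ≥ 25 | 45, 0.45) = 0.102
- P(X ≥ 25 | 48, 0.45) = 0.200

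**6. Effect of the fix on the design.** Dating the SAP earlier leaves N = 42, cut-off 25, alpha 0.0415 and power 0.818 unchanged. If the FAS is settled as a set of another size, the critical value must follow it (for example 27/45 or 28/48).

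**The case against.** The strongest reply is that the confirmatory analysis is already in the protocol: endpoint, test, level, missing-data rule, primary set and number of analyses. SAP timing does not govern these, and finalising a SAP before lock is common practice. All of this stands. A reader might infer from 8.3 that the confirmatory 5% test as a whole is open to data-driven choice. The documents do not support that.

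A reader might also take 8.1.4 as permission for the SAP to alter the phase II primary analysis. That goes too far. The sentence follows directly on the statement that the phase I analysis is descriptive, section 8.2 does not repeat it, and it can be read as a duty to document. Section 12 requires an amendment in any case. What remains is that 8.1.4 and section 12 name different vehicles for a change, which should be tidied.

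Third, the 7.7% could be called the error of breaking the protocol, since treated failures cannot be dropped from the FAS. For patients exposed to both drugs that is right. It does not answer the case of patients who stop on days 1 to 3, because 4.4.1 and 8.2.2.1 assign them differently and either choice can cite the protocol.

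Finally, the labelling gap in 8.3 is narrow. Section 8.2.4 already calls everything except the primary endpoint descriptive and exploratory, and no interim analysis is planned in phase II. That limits the harm but does not make the wording right.

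**Conclusion.** The point holds as a cheap improvement, limited to the denominator. Three statements about the FAS and its cut-off do not agree, and 8.3 lets the SAP settle them after the open-label responses are known, by about 22 months if lock follows last patient out.

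The size depends on what happens in the trial. The error of up to 7.7% needs at least two failures who stop before cytarabine; with one, the decision at 24 responders does not change. Choosing between analysis sets with and without phase I patients costs little: 4.5% with three added and 5.5% with six. The larger figures, 10.2% and 20.0%, arise only if the cut-off of 25 is applied unchanged to 45 or 48 patients. That would follow from reading the Synopsis rule onto the FAS of 8.2.2.1; the exact test in 8.2.5.1, applied to the actual denominator, would not do it.

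None of this shows that the confirmatory test is unprotected in general or that the design figures are wrong.

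**What to change.** - **Section 8.3:** require the SAP to be finalised, signed and dated before the first phase II remission assessment (V8). In the sentence on unplanned analyses, delete the condition about timing relative to lock, so that any analysis not pre-specified is labelled exploratory whenever it was run.
- **Section 8.1.4:** state that the SAP details the protocol analyses and that changes to them need an amendment under section 12.
- **Sections 4.4.1 and 8.2.2.1 and the Synopsis:** adopt one FAS definition. Say whether a patient who received venetoclax but no cytarabine is in, and whether phase I patients at the MTD count in the primary test. State the critical value for the resulting denominator, or state that the exact test is applied to the actual FAS size and that 25 holds only for 42.

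The cost is wording and SAP work done earlier. No patients or data are added, and redating the SAP changes no design figure.

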# **9 Data handling and quality assurance**

## **9.1 Data recording**

It is the responsibility of the investigator to perform the clinical study in accordance with the GCP guidelines, the AMG, and the clinical study protocol. All data have to be recorded correctly in the eCRF by authorized persons only. This also includes data of persons who were excluded from the clinical study.

The investigator documents the participation of a person at the Screening/Enrollment Log and Subject Identification Log. These lists are meant to identify participating patients at a later point of time. It includes the complete name, the date of birth, and the date of inclusion into the clinical study. The Subject Identification Log remains in the study center after the study is finished. In addition, participation in the clinical study has to be documented in the patient's chart (including informed consent process, screening, study medication, participant number, start and end of the clinical study).

It has to be ensured that the person responsible for documentation in the eCRF can be identified. Therefore, a list with signatures and abbreviations (site signature log) is kept in the ISF.

### **9.1.1 Electronic Case report form (eCRF)**

All data of the participants have to be recorded in electronic CRFs.

The Investigator is responsible for all data of the participant to be documented in the electronic Case Report Form (eCRF) exclusively designed for the study immediately, correctly and completely.

Corrections in the eCRF are to be conducted only by authorized personnel and to be justified. The former database entry will remain retrievable. All dates and corrections are recorded automatically concerning date, time point and person.

### **9.1.2 Investigator Site File**

The SAL Studienzentrale provides the Investigator Site File to the study center. The ISF includes all documents that are required for the clinical study. During monitoring, the ISF will be checked regularly for completeness and actuality. After the clinical trial is finished or stopped, the ISF has to be stored for at least 10 years.

### **9.1.3 Data Storage**

#### Responsibilities of the Sponsor

As required by law, all important study documents have to be stored by the sponsor for at least 10 years after the clinical trial was finished or stopped.

#### Responsibilities of the Investigator

All documents which are related to the clinical study and to the distribution of the study medication (e.g. CRFs, written informed consent forms, study medication lists and other relevant material) have to be stored for at least 10 years.

Source data like patients' charts, laboratory analyzes, and other original data have to be stored for the longest possible time that is usual practice at the investigator's site, at least for 10 years.

## **9.2 Monitoring**

The investigator agrees that the monitor will visit the study center in appropriate intervals. During these visits, the monitor will check the quality of the data recording and ensure that the study center adheres to the timeframe as set in the study protocol. The investigators agree to provide any relevant information and documentation whenever requested by the monitor. This includes access to all original study documents and source data including access to electronic source documents if necessary.

It is the responsibility of the investigator to keep the participant's chart as complete as possible (e.g. history, concomitant diseases, inclusion in the clinical study, visit dates, results of laboratory tests, distribution of the study medication, and adverse events). Source data are checked and compared with entries in the database. The participant has given consent with this procedure by signing the patient information and written informed consent form.

Additional tasks of the monitor are:

- To check, whether the study center fulfills requirements of the clinical study (e.g. participant population, technical equipment, adequate storage of medication),

- Instruction of the investigators and personnel for the clinical trial,
- To check the ISF for completeness and actuality,
- Documentation of the status of the participant,
- Matching of original data,
- To check SAE reports according to regulations.

The monitor has the responsibility to treat all information confidentially and to safeguard the integrity and personal privacy of the study participants.

### **9.3 Data processing**

Data management is performed by the Data Center of the SAL Studienzentrale and the KKS Dresden by means current version of study software MACRO. Data quality will be checked by programmed range checks, validity checks, and consistency checks. In addition, a manual/visual data check for medicinal plausibility is done according to GCP guidelines. There might be discrepancies, which are to be clarified by authorized persons by means of the study software.

After the study is finished and before data are analyzed, a meeting will be held between the sponsor and statistician. When the database has been declared to be complete and accurate, it will be locked. This procedure has to be documented.

### **9.4 Audit and inspection**

To guarantee the conduct of the clinical study according to GCP guidelines, sponsor audits and governmental inspections can be performed.

During the audits and inspections, the following aspects are checked:

- Conduct of the study according to the protocol,
- Data validity, patient safety
- Quality of the study according to GCP guidelines.

## **10 Premature termination of the study**

The sponsor has the right to close this study (or, if applicable, individual segments thereof [e.g. study arms, dose steps, centers]) at any time, which may be due but not limited to the following reasons:

- If risk-benefit ratio becomes unacceptable owing to, for example, safety findings from this study (e.g. SAEs)
- Results of any interim analysis
- Recommendations from steering committee
- New scientific discoveries from literature or results from other clinical studies

- Results of parallel animal studies (on e.g. toxicity, teratogenicity, carcinogenicity, or reproduction toxicity).
- If the study conduct (e.g. recruitment rate, dropout rate, data quality, protocol compliance) does not suggest a proper completion of the study within a reasonable period.

The investigator has the right to close his / her center at any time.

For any of the above closures, the following applies:

- Closures should occur only after consultation between involved parties.
- All affected institutions (e.g. IEC(s) / IRB(s); competent authority(ies); study center(s)) must be informed as applicable according to local law.
- All study materials (except documentation that has to remain stored at site) must be returned to the sponsor. The investigator will retain all other documents until notification given by the sponsor for destruction.
- In case of a partial study closure, ongoing subjects, including those in post-study follow-up, must be taken care of in an ethical manner.

Details for individual subject's withdrawal can be found in section 4.4.

## **11 Ethical and legal aspects**

### **11.1 Ethical and legal conduct of the study**

The procedures set out in this protocol, about the conduct, evaluation, and documentation of this study, are designed to ensure that the sponsor and investigator abide by GCP Guidelines and under the guiding principles detailed in the Declaration of Helsinki. The study will also be carried out in keeping with applicable local law(s) and regulation(s).

Strict adherence to all specifications laid down in this protocol is required for all aspects of study conduct; the investigator may not modify or alter the procedures described in this protocol.

Modifications to the study protocol will not be implemented by either the sponsor or the Coordinating investigator without agreement by both parties. However, the investigator or the sponsor may implement a deviation from, or a change of, the protocol to eliminate an immediate hazard(s) to the study subjects without prior IEC / IRB / sponsor approval / favorable opinion. As soon as possible, the implemented deviation or change, the reasons for it and if appropriate the proposed protocol amendment should be submitted to the IEC / IRB / sponsor. Any deviations from the protocol must be explained and documented by the investigator.

